9.3.1 Exposures

The drug of interest is Jardiance® with the active ingredient empagliflozin. Within this study, there are two HF patient cohorts: patients receiving first prescription of empagliflozin and those who have been prescribed a drug with a different mechanism of action for the treatment of HF.

During this study, it is planned to observe for each patient who receives a first prescription of empagliflozin a treatment period of approximately 24 weeks. Patients not treated with empagliflozin will not be observed further after visit 1.

The recommended daily dose of empagliflozin for treatment of heart failure is 10 mg once daily.

9.3.2 Outcomes

This NIS will describe contemporary, real-world patterns of patient characteristics, clinical disease presentation, and therapeutic regimen chosen in participants with chronic HF in CEE countries. Additionally, PRO is assessed by use of the disease specific KCCQ. These data will be collected at visit 1 of all registered patients.

The primary objective is to document and analyze QoL data from patients with HF receiving first treatment with empagliflozin in daily routine care. For this approach, the disease specific KCCQ is used to examine changes from index date 1 to index date 2 (= 24 weeks after study index date 1) in these patients. The primary outcome will be evaluated on patients receiving initial prescription of empagliflozin at visit 1 and who have filled in the KCCQ at visit 1 and visit 2.

[figure not shown]
The primary and secondary outcomes do not touch any safety questions.

9.3.2.1 Primary outcomes

Change of each of the Kansas City Cardiomyopathy Questionnaire (KCCQ) scores [clinical summary score (CSS), total symptom score (TSS), overall summary score (OSS)] from index date 1 to index date 2 (= 24 weeks after index date 1) in patients newly treated with empagliflozin according to routine practice

9.3.2.2 Secondary outcomes

- Change of the New York Heart Association (NYHA) Class from index date 1 to index date 2 (= 24 weeks after index date 1) in patients newly treated with empagliflozin
- Capture of real-world patterns of patient characteristics, clinical disease presentation and therapeutic regimen chosen in participants with chronic HF as well as of patient reported outcome at visit 1.

**9.3.3 Covariates**

Covariates for adjustment will include patient demographics and disease characteristics. These will be discussed in the Statistical Analysis Plan (SAP).

9.4 DATA SOURCES

Medical records collected through routine clinical care will be used to assess the inclusion/exclusion criteria of patients as well as for patient demographics, collection of current HF medication, concomitant diseases, and concomitant medication, as well as for the health data of the patient at visit 2.

The KCCQ will be provided as paper version by the treating physician or trained site staff to the patient to be filled out in writing at visit 1 (all patients) and visit 2 (patients with initial empagliflozin treatment only).

9.5 STUDY SIZE

With no formal a-priori hypotheses, this observational study uses a hypothesis-free approach focused on descriptive analyses. Thus, no formal sample size calculation is provided. The study is designed to describe the use of empagliflozin and PRO in clinical routine. In the 8 participating countries sites in urban as well as rural areas will be included. The nationwide distribution of the participating sites and the number of 4600 patients enrolled are intended to ensure that the data

collected are representative. Based on random identification, it is expected that about 3300 patients will receive empagliflozin. The large sample size overall was chosen to support a large range of analyses from general scientific questions to specific regional or subgroup questions with sufficient precision. A minimum target number of 100 patients per country is chosen to provide reasonable sample size for scientific questions applicable across countries and subgroups of interest. The sample size will ensure that the descriptive data are sufficiently precise and meaningful at a country or subgroup level.

9.6 DATA MANAGEMENT

The data management plan (DMP) is summarized below. Full details of the data management plan are documented in a separate NIS-Data Management and Review Plan (NIS-DMRP).

The NIS-DMRP will describe all functions, processes, and specifications for data collection, cleaning and validation. The contract research organization (CRO) [REDACTED] is assigned for electronic data capture (EDC) system development. The electronic Case Report Forms (eCRF) are part of the EDC system which allows documentation of the relevant study variables by all participating sites in a standardized manner. The eCRF will include programmable edits to obtain immediate feedback if data are missing (also negative answers, unknown), out of range, illogical or potentially erroneous. These rules may encompass simple checks such as range validation or presence/absence of data. Concurrent manual data review by personnel of data management of the CRO may be performed based on parameters dictated by the DMP. Ad hoc queries to the sites may be generated and followed up for resolution.

The database will be housed in a physically and logically secure computer system maintained in accordance with a written security policy. The system will meet the standards of the International Committee on Harmonization guideline E6R1 regarding electronic study data handling and the safety requirements of the FDA (US Food & Drug Administration) concerning systems for the data acquisition of clinical studies in accordance with "Title 21 Code of Federal Regulations (21 CFR Part 11): Electronic Records; Electronic Signatures. Patient confidentiality will be strictly maintained.

9.7 DATA ANALYSIS

Statistical analysis will be performed by [REDACTED]).

The statistical analysis plan (SAP) for the study is summarized below. Full details of the statistical analysis will be documented in the SAP, which will be finalized before the end of data collection.

In general, all analyses will be carried out by using descriptive and exploratory statistical methods including exploratory confidence intervals and p-values. For the analyses SAS® software version 9.4 or higher will be used.

All data captured at visit 1 will be analyzed on all registered patients [Full analysis set (FAS)]. All patients who have received at least one dose of empagliflozin for HF and have filled in KCCQ at time points 'index date 1' and 'index date 2 (= week 24 after index date 1)' will be included in the 'primary endpoint set' which will be used for primary endpoint analysis.

Safety set: All patients who received empagliflozin at least once will be used for safety and further analyses.

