9.7.1 Main analysis

Analysis of the primary outcome

- Change of each of the Kansas City Cardiomyopathy Questionnaire (KCCQ) scores [clinical summary score (CSS), total symptom score (TSS), overall summary score (OSS)] from index date 1 to index date 2 (= 24 weeks after index date 1) in patients newly treated with empagliflozin according to routine practice

will be performed according to the analysis manual for the KCCQ. Changes in the KCCQ scores will be calculated for each patient. Results will be presented as N, mean, standard deviation, median, minimum and maximum values as well as number of missings as extra column. A change of 5 points of OSS will be considered as clinically meaningful.

Change from index date 1 in clinical summary score for HF symptoms and physical limitations domains of the KCCQ at week 24 will be evaluated further by subgroup analyses based on age at index date 1, gender, country, baseline LVEF (rEF, mpEF pEF), and status of diabetes mellitus at visit 1. All recorded data for efficacy up to week 24 will be included.

[figure not shown]
Analysis of the secondary outcome

- Change of the New York Heart Association (NYHA) Class from index date 1 to index date 2 (= 24 weeks after index date 1) in patients newly treated with empagliflozin
tabulation of relative and absolute frequencies will be presented.

For the analysis of the secondary outcome

- Capture of real-world patterns of patient characteristics, clinical disease presentation and therapeutic regimen chosen in participants with chronic HF as well as of patient reported outcome at visit 1

tabulations of relative and absolute frequencies will be presented. Comparison of data at visit 1 between patients receiving empagliflozin or not for treatment of HF will be performed by Chi-quadrat-test or Mann-Whitney-U-test.

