3. PURPOSE AND SCOPE

As per ICH E9 [1] (International Conference on Harmonisation), the purpose of this document is to provide a more technical and detailed elaboration of the principal features of the analysis described in the protocol, and to include detailed procedures for executing the statistical analysis of the primary and secondary variables and other data.

This Statistical and Epidemiological Analysis Plan (SEAP) assumes familiarity with the Observational plan, including Protocol Amendments. In particular, the SEAP is based on the planned analysis specification as written in Observational plan Section 9.7 “Data Analysis”. Therefore, SEAP readers may consult the Observational plan for more background information on the study, e.g., on study objectives, study design and population, definition of measurements and variables, planning of sample size, randomization.

SAS® Version 9.4 (or later version) will be used for all standard analyses.

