10. DATA ANALYSIS

Full analysis set (FAS): All registered patients who gave informed consent.

All data captured at visit 1 will be analysed for FAS.

Primary endpoint set (PES): All patients, who received at least one dose of empagliflozin for HF and have filled in KCCQ at time points index date 1 and 24 week follow-up visit. The primary endpoint will be analysed for PES.

Safety set (SAF): All patients of FAS who received empagliflozin at least once. SAF will be used for safety and further analyses.

For continuous variables number of values, mean, standard deviation, minimum, 5th percentile, 25th percentile, median 75th percentile, 95th percentile, maximum and number of missing values will be presented. For categorical variables the number and percentage with a category for missing will be given.

Percentages will be rounded to two decimal places.

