10.1 MAIN ANALYSIS

Analysis of the primary outcome

- Change of each of the Kansas City Cardiomyopathy Questionnaire (KCCQ) scores [clinical summary score (CSS), total symptom score (TSS), overall summary score (OSS)] from index date 1 to index date 2 (= 24 weeks after index date 1) in patients newly treated with empagliflozin according to routine practice

will be performed according to the analysis manual for the KCCQ. Changes in the KCCQ scores will be calculated for each patient. Results will be presented as N, mean, standard deviation, median, minimum and maximum values as well as number of missings as extra column. A change of 5 points of OSS will be considered as clinically meaningful.

In addition, change from index date 1 in clinical summary score for HF symptoms and physical limitations domains of the KCCQ at week 24 will be evaluated by subgroups based on age at index date 1 (<50/50-<65/65-<75/≥75 years as well as <65/≥65 years), gender, country, baseline LVEF (HFrEF, HFmrEF HFpEF), and status of diabetes mellitus at visit 1. All recorded data for efficacy up to week 24 will be included.

For analysis of the secondary outcome

- Change of the New York Heart Association (NYHA) Class from index date 1 to index date 2 (= 24 weeks after index date 1) in patients newly treated with empagliflozin tabulation of relative and absolute frequencies will be presented as well as a shift table.

For the analysis of the secondary outcome

- Capture of real-world patterns of patient characteristics, clinical disease presentation and therapeutic regimen chosen in participants with chronic HF as well as of patient reported outcome at visit 1

tabulations of relative and absolute frequencies will be presented. Comparison of data at visit 1 between patients receiving empagliflozin or not for treatment of HF will be performed by Chi- quadrat-test or Mann-Whitney-U-test or Student t-Test.

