ANNEX 1. ADDITIONAL INFORMATION

The shell of the tables, figures and listings will be provided as a separate document..

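### Does the primary KCCQ outcome need a confidence interval written into the statistics lists, and a calculation behind the country-level precision statement?

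*Protocol*

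**What the plan says.** Protocol 9.7 describes the analysis in general terms: "In general, all analyses will be carried out by using descriptive and exploratory statistical methods including exploratory confidence intervals and p-values". It gives no confidence level and leaves full details to the SAP. SAP 3 ties itself to that section, stating that "the SEAP is based on the planned analysis specification as written in Observational plan Section 9.7".

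For the primary outcome (change in CSS, TSS and OSS), Protocol 9.7.1 and SAP 10.1 use the same sentence: "Results will be presented as N, mean, standard deviation, median, minimum and maximum values as well as number of missings as extra column". For continuous variables in general, SAP 10 asks for "number of values, mean, standard deviation, minimum, 5th percentile, 25th percentile, median 75th percentile, 95th percentile, maximum and number of missing values". SAP 10.1 adds that the "clinical summary score for HF symptoms and physical limitations domains of the KCCQ at week 24 will be evaluated by subgroups", and country is one of those subgroups. The p-values do have a home: "Comparison of data at visit 1 between patients receiving empagliflozin or not for treatment of HF will be performed by" named tests. SAP Annex 1 says "The shell of the tables, figures and listings will be provided as a separate document".

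Protocol 9.5 states that there is no formal sample size calculation because the study is descriptive. It sets a minimum of 100 patients per country and concludes: "The sample size will ensure that the descriptive data are sufficiently precise and meaningful at a country or subgroup level".

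**The concern.** Protocol 9.7 announces both p-values and intervals. Tests are specified for the visit 1 cohort comparison, but no analysis in the available text is assigned an interval, not even the primary outcome, where one is most useful. A programmer who took SAP 10.1 as a complete list would print none. Percentiles and SD describe the spread between patients, not the uncertainty of a mean, so a small country's mean would appear in the same format as a large country's.

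Protocol 9.5 seems to compound this. Its assurance about countries comes with no SD, target width or allowance for missing data. The minimum of 100 appears to count all enrolled patients, whereas KCCQ change can be computed only for empagliflozin patients with a questionnaire at both visits. At stake is how much weight a reader gives to the country means. No test or decision depends on it.

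**Working it through.** **1. The lists compared.**

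| Place | Statistics | Interval? |
|---|---|---|
| Protocol 9.7 | general approach for all analyses | yes, exploratory |
| Protocol 9.7.1 and SAP 10.1 (primary outcome) | N, mean, SD, median, min, max, missing | none named |
| SAP 10 (continuous variables) | the same plus 5th, 25th, 75th and 95th percentiles | none named |

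The primary-outcome list in SAP 10.1 also omits the percentiles that SAP 10 requires for every continuous variable. The SAP 10.1 list is therefore not exhaustive, and absence from it does not show that a statistic will be left out.

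**2. Can the interval be recovered?** Yes. The half-width is t(0.975, n−1) × SD / √n, and both N and SD are in every list.

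**3. Scale of the country-level question.** The plan states no precision figure, so there is none to reproduce.

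Inputs from the documents:
- about 4600 patients, about 3300 of them on empagliflozin, 8 countries, minimum 100 per country (Protocol 9.2.1 and 9.5).

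Assumptions, none given in the documents:
- SD of KCCQ change 15, 20 or 25 points;
- 0, 20 or 30% of visit 2 questionnaires missing;
- the same empagliflozin share in every country;
- simple random sampling within country.

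Share on empagliflozin: 3300/4600 = 0.717. A country with 100 enrolled then has 100 × 0.717 ≈ 72 empagliflozin patients; 71.7 × 0.8 ≈ 57 and 71.7 × 0.7 ≈ 50 remain after missing questionnaires.

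| Case | n | SD 15 | SD 20 | SD 25 |
|---|---|---|---|---|
| Country at minimum, none missing | 72 | 3.5 | 4.7 | 5.9 |
| 20% missing | 57 | 4.0 | 5.3 | 6.6 |
| 30% missing | 50 | 4.3 | 5.7 | 7.1 |
| If the 100 are all on empagliflozin, none missing | 100 | 3.0 | 4.0 | 5.0 |
| Same, 20% missing | 80 | 3.3 | 4.5 | 5.6 |
| Same, 30% missing | 70 | 3.6 | 4.8 | 6.0 |

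An average country has 3300/8 ≈ 412 empagliflozin patients, giving 1.9 points at SD 20. The overall estimate with n = 3300 gives 0.7.

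**4. Against a yardstick.** The only threshold in the plan is 5 points, stated for OSS, whereas the country analysis is of CSS, so it is a rough guide. Of the nine values in the first three rows, four are below 5. In the second three rows, seven of nine are (the n = 100, SD 25 value is 4.96 before rounding). Whether a country at the floor is sufficiently precise depends on inputs and a standard that the plan does not set.

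**5. Is any country expected at the floor?** The documents do not say so. An even split is 4600/8 = 575 enrolled per country.

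**The case for a change.** The strongest case for a change is that Protocol 9.7 leaves the details to the SAP and the SAP then says nothing about intervals. The main purpose of the study is to estimate a mean change, and an interval is the usual way to show how well a mean is known. With half-widths running from about 2 points in an average country to about 5 or 6 in a country at the floor (SD 20), one extra table column would help the reader at almost no cost.

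The description of the text stands: no list names an interval. Three things take away its force. First, the 9.7 sentence describes methods in general and still applies, because the SAP is built on that section and does not revoke it. An analyst who adds an exploratory 95% interval is following the plan. Second, such a column is normally fixed in the table shells, which are a separate document and were not available here. Third, N stands beside each mean, so a country with 50 patients is visibly different from one with 400.

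On Protocol 9.5, the missing calculation is an openly declared choice, and an acceptable one in a study without hypotheses. The sentence also covers descriptive data at large, including visit 1 data on all enrolled patients. What remains is a loosely worded assurance about KCCQ change in countries near the minimum.

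The abstract gives 7000 patients where Protocol 9.2, 9.2.1 and 9.5 and SAP 6.2 give 4600. This looks like a figure not updated in the abstract. It is a separate matter and adds nothing here, since 9.5 itself uses 4600 and pairs 3300 with it.

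**Conclusion.** No change to the plan follows. The missing interval is a gap in detail that analysts can fill from Protocol 9.7. Followed literally, the plan still reports a sound N, mean and SD for each score and for each planned CSS subgroup; the interval is one line of arithmetic away and no conclusion turns on it. For the overall result it would be about ±0.7 points at an assumed SD of 20.

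The precision statement in Protocol 9.5 is unquantified but not shown to be false. In a country exactly at the minimum, the half-width runs from 3.5 to 7.1 points if the 100 counts all enrolled patients, and from 3.0 to 6.0 if it counts empagliflozin patients only. Both ranges rest on the assumed SDs of 15 to 25, 0 to 30% missing questionnaires and no clustering by site; the first also assumes an equal treatment mix across countries. Writing a calculation into 9.5 would alter neither enrolment, nor the country targets, nor any analysis.

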9.7.1 Main analysis

Analysis of the primary outcome

- Change of each of the Kansas City Cardiomyopathy Questionnaire (KCCQ) scores [clinical summary score (CSS), total symptom score (TSS), overall summary score (OSS)] from index date 1 to index date 2 (= 24 weeks after index date 1) in patients newly treated with empagliflozin according to routine practice

will be performed according to the analysis manual for the KCCQ. Changes in the KCCQ scores will be calculated for each patient. Results will be presented as N, mean, standard deviation, median, minimum and maximum values as well as number of missings as extra column. A change of 5 points of OSS will be considered as clinically meaningful.

Change from index date 1 in clinical summary score for HF symptoms and physical limitations domains of the KCCQ at week 24 will be evaluated further by subgroup analyses based on age at index date 1, gender, country, baseline LVEF (rEF, mpEF pEF), and status of diabetes mellitus at visit 1. All recorded data for efficacy up to week 24 will be included.

[figure not shown]
Analysis of the secondary outcome

- Change of the New York Heart Association (NYHA) Class from index date 1 to index date 2 (= 24 weeks after index date 1) in patients newly treated with empagliflozin
tabulation of relative and absolute frequencies will be presented.

For the analysis of the secondary outcome

- Capture of real-world patterns of patient characteristics, clinical disease presentation and therapeutic regimen chosen in participants with chronic HF as well as of patient reported outcome at visit 1

tabulations of relative and absolute frequencies will be presented. Comparison of data at visit 1 between patients receiving empagliflozin or not for treatment of HF will be performed by Chi-quadrat-test or Mann-Whitney-U-test.

9.7.3 Safety analysis

All adverse drug reactions (ADRs) (serious and non-serious), all AEs with fatal outcome, hospitalizations due to HF as collected per study protocol will be included and summarized in the final study report.

Adverse events will be coded using the Medical Dictionary for Regulatory Activities (MedDRA) coding dictionary. Standard BI summary tables and listings will be produced. All patients treated with empagliflozin for HF will be included in the safety analysis. In general, safety analyses will be descriptive in nature.

Statistical analysis and reporting of adverse events will concentrate on treatment-emergent adverse events.

All adverse events occurring on empagliflozin treatment plus 7 days will be considered 'treatment-emergent'. Deterioration of pre-existing conditions will also be considered 'treatment-emergent'.

Frequency, severity, and causal relationship of adverse events will be tabulated by system organ class and preferred term after coding according to the current version of MedDRA.

9.8 QUALITY CONTROL

The quality control, review, and monitoring plan are summarized below. Greater details are documented in the NIS-DMRP.

All participating sites will receive a comprehensive study site file with all information on the NIS. Site staff will be trained on the study procedures and on handling of the eCRF before documentation of the first patient by a mandatory webinar or on-site, whatever will be more feasible (e.g. influenced by pandemic situation). Training will be documented in the study site file.

To improve and secure data quality, automatic data checks (eChecks) upon data entry will be done within the eCRF. In the eCRF, plausible ranges of values for numeric data entries as well as logical data entries and listings will be provided for each entry field. Based on this, checks on completeness and plausibility will be performed upon data entry in the eCRF.

Validity of data entry thus is ensured by integrated validation checks performed by the system, indicating missing or implausible entries to the document list or investigator. All corrections will be visible from the systems audit trail. Data management activities by means of manual query processes might be implemented as defined in the DMP to increase data integrity.

To provide further quality assurance of the documented patient observations, routine monitoring will take place at the site with the highest number of patients currently enrolled two months after the First Patient In (FPI) in the respective country. If on-site visits are not possible due to pandemic situation, remote quality review may be performed. Risk-based monitoring or for-cause audit will be performed based on the key risk indicators in case of decreasing data quality (i.e. of missing data, data discrepancies, protocol violations, etc.). Details will be specified in the study monitoring plan.

